**CCI**

#### **3.2 Study Design**

This is a multicenter, randomized, open label exploratory study, conducted in the US and Canada, evaluating the efficacy and safety of enzalutamide for extension of time to prostate cancer progression (pathological or therapeutic) in subjects with clinically localized, histologically proven prostate cancer that is categorized as low risk or intermediate risk and who are under AS. A total of 222 subjects from approximately 50 centers will be enrolled. Subjects are eligible if they were diagnosed within 6 months of screening and have been on AS. A minimum of ten cores from transrectal ultrasound-guided prostate biopsy (mpMRI targeted versus non-mpMRI targeted) are required; confirmatory biopsy before entering the study is not required and is done at the discretion of the investigator.

Low risk is defined as T1c-T2a, PSA $<$ 10, N0, M0 (or presumed N0, M0 if computerized tomography [CT]/bone scan not done due to low risk of metastases), GS  $\leq$  6, ECOG status  $\leq$  2 and estimated life expectancy  $>$  5 years. Intermediate risk is defined as T2b-T2c, PSA $<$ 20, N0, M0 (or presumed N0, M0 if CT/bone scan not done), GS  $\leq$  7 (3+4 pattern only), ECOG status  $\leq$  2 and estimated life expectancy  $>$  5 years.

Prostate cancer progression is defined as either therapeutic progression or pathological progression. Therapeutic progression is defined as the earliest occurrence of primary therapy for prostate cancer (prostatectomy / radiation / focal therapy / systemic therapy). Pathological progression is defined as increase in primary or secondary Gleason pattern by  $>$  1 or higher

proportion of cancer positive cores (>15% increase). Subjects will be stratified by low versus intermediate risk and type of biopsy performed (mpMRI targeted versus non-mpMRI targeted).

Subjects will be randomized (1:1) either to receive treatment with enzalutamide (160 mg), administered as four 40 mg capsules, by mouth, once daily or to AS during the one year study treatment period. Following the one year treatment period, all subjects will be followed for one additional year. Subjects will be followed up every 3 months for these 2 years, after which follow-up will either be every 6 months or unscheduled until the last subject finished their 2 year follow-up. Serum PSA will be measured at baseline and every 3 months during subsequent follow-up visits.

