## 4 SAMPLE SIZE

This study is designed to evaluate time to prostate cancer progression (pathological or therapeutic progression) as the primary endpoint. The overall two-sided type I error for this study is set at 0.05 level. The characteristics of time to prostate cancer progression (pathological or therapeutic progression) are used to determine the total sample size and overall duration.

A sample size of 222 subjects randomized in a 1 to 1 manner accrued over one year, a study duration of 3 years, loss-to follow-up of 16%, an assumed underlying hazard ratio of 0.52 and a three year median time-to-progression for the Control group (0.2310 rate) will result in 72 events (Fleshner et al., 2012). This sample size is sufficient to power this study at 80% with a two-sided type I error rate of 5%.

The assumed hazard ratio of 0.52 is consistent with Fleshner et al. (2012). Specifically, the Fleshner study is powered to detect a 39% failure rate reduction in the treated group with respect to a three year 45% failure rate in the control group. We used a more conservative 30% failure rate reduction for the treated group and a 50% three year failure rate for the control group. This resulted in parameter estimates of 0.2310 for the Control group and 0.1189 for the Treatment group, and thus, resulted in the hazard rate of 0.52.

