### 7.4.1 Analysis of Primary Endpoint(s)

The primary efficacy endpoint is time to prostate cancer progression (pathological or therapeutic), and the hypothesis for analysis is:

$H_0$ : The time to progression for Enzalutamide and Active Surveillance (AS) are the

same  $H_1$ : The time to progression for Enzalutamide and AS are not the same

Median and 95% confidence intervals for time to prostate cancer progression (pathological or therapeutic) will be calculated with the Kaplan-Meier (KM) method for each treatment group. Subjects with no cancer progression at the time of trial completion, discontinuation or death will be censored at the last assessment date. Additionally, subjects switching therapy during the study will be censored at the time of the initial therapy switch, but subjects discontinuing therapy will not be censored until the time of study discontinuation. If less than 50% of subjects progress by study cut-off time, the 25th percentile and its two-sided 95% confidence interval will be reported. KM plots will be generated.

Treatment group differences between enzalutamide versus AS will be based on a Cox regression model. The resulting Hazard ratio (enzalutamide/AS) and 95% confidence interval will be included in the summary. Censoring assumptions will follow the same rules as applied for the KM estimates. Fixed effects for the model will include the treatment groups, randomization stratification factors [prostate cancer risk (low/intermediate), type of biopsy performed (mpMRI targeted/non mpMRI targeted)], age, race, and time since prostate cancer diagnosis. Additionally, a random effect of site will be included in the model.

The association between the survival time, log of time to disease progression, and survival probability, log negative log, will be investigated graphically by Cox proportional-hazards models. If the proportional hazards assumption is violated, appropriate remedial methods will be investigated and applied.

Data listings will be provided.

In addition to an overall analysis, the primary and secondary analyses will be repeated for pathological progression and therapeutic progression, individually.

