### **7.4.2 Analysis of Secondary Endpoints**

#### **7.4.2.1 Cancer Biopsy Incidence and Secondary Rise in PSA**

The incidence of negative biopsy for cancer and secondary rise in serum PSA will be summarized with frequencies and percentages at one and two years by treatment group, subgroups and overall.

Treatment comparisons will be performed using the exact binomial distribution as well as the normal approximation to the binomial distribution. Inferences will include 95% confidence intervals of the odds ratio for each endpoint between treatment groups at both Year 1 and Year 2 for biopsies and for each of Years 1 and 2 and end of study for PSA. Comparison between enzalutamide and AS will be evaluated by logistic regression using the treatment groups, randomization stratification factors [prostate cancer risk (low/intermediate), type of biopsy performed (mpMRI targeted/non mpMRI targeted)], age, race, and time since prostate cancer diagnosis as fixed effects and site and subject as random effects.

Time to PSA progression will be analyzed with the same methods as detailed for the primary endpoint analysis in Section 7.4.1.

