#### **7.4.2.3 Cancer Positive Cores**

[figure not shown]
Percent of cancer positive cores, assessed using the number of systemically-sampled prostate regions and any targeted regions with at least one positive core (see Section 6.4 for details), will be analyzed at Screening, 12, and 24 months.

Analyses of treatment group differences for the change from baseline composite score will be analyzed with a Mixed Model Repeated Measures (MMRM) model using subject and site as a random factors. For the variance- covariance matrix, compound symmetry (CS), autoregressive (AR1) and unstructured (UN) will be assessed and the best fit will be chosen based on Akaike Information Criteria (AIC) or AICC (correction for finite sample sizes). Degrees of freedom will be approximated using the Kenward-Roger method. Fixed effects will include treatment group, the stratification factors [prostate cancer risk (low/intermediate) and type of biopsy performed (mpMRI targeted/non- mpMRI targeted)], time, time-by-treatment interaction and baseline composite score. Estimates will include 95% confidence

intervals of least square means (LS Means) for each treatment group by nominal time point and overall. P-values will be adjusted using the bonferroni-holm method to adjust for multiplicity. Additionally, assessments of treatment group differences will be made at 3, 6, 12, and 24 months, as well as for the overall model.

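### The progression, negative-biopsy and PSA models omit baseline percent positive cores and continuous baseline PSA, forgoing some efficiency and protection against chance imbalance; the analyses remain valid.

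*SAP*

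**What the plan says.** - **Primary Cox model (SAP 7.4.1).** The fixed effects are treatment, risk group (low or intermediate), biopsy type (mpMRI-targeted or not), and then "age, race, and time since prostate cancer diagnosis. Additionally, a random effect of site will be included in the model".
- **Progression logistic model (7.4.1.1).** It reuses the covariates and random effect of the primary model.
- **Negative biopsy and PSA rise (7.4.2.1).** Logistic models with treatment, the two stratification factors, and "age, race, and time since prostate cancer diagnosis as fixed effects and site and subject as random effects". Time to PSA progression follows the methods of 7.4.1.
- **Eligibility (3.2).** "Subjects are eligible if they were diagnosed within 6 months of screening and have been on AS".
- **Risk group (3.2, 3.3).** Low risk requires T1c-T2a, PSA below 10 and Gleason score 6 or less. Intermediate risk covers T2b-T2c, PSA below 20 and Gleason up to 7 (3+4 only). Low-risk men may make up as much as 80% of the study. The number or share of positive cores plays no part in the definition.
- **Endpoints (6.4).** Pathological progression is a worsening of Gleason pattern or a rise in the proportion of positive cores. PSA rise is judged against baseline, against nadir, or by an absolute increase.
- **Positive-cores model (7.4.2.3).** The repeated-measures model lists "time, time-by-treatment interaction and baseline composite score" among its fixed effects.

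**The concern.** Several of these endpoints are defined as change from a baseline that the models do not contain. A rise in the share of positive cores starts from the entry biopsy. Whether a later biopsy is negative plausibly depends on how much of the gland was positive at entry. For PSA, a 25% rise over baseline equals 2 ng/mL at a baseline of 8 (0.25 x 8 = 2). If the absolute increase is also counted from baseline, the percentage rule is the easier one to meet below 8 and the absolute rule above it, so the chance of meeting the definition depends on baseline PSA.

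The only disease measure in the models beyond the two strata is time since diagnosis, which eligibility confines to a short range. If the omitted baselines are prognostic, adjusting for them would make the treatment comparison more efficient and would protect a trial of 111 men per arm against a chance difference in those baselines.

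**Working it through.** **1. The plan's own figure (Section 4).** Inputs: "A sample size of 222 subjects randomized in a 1 to 1 manner accrued over one year", three years in total, 16% loss to follow-up, two-sided 5%, 80% power, and "parameter estimates of 0.2310 for the Control group and 0.1189 for the Treatment group".

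- Hazard ratio: 0.1189 / 0.2310 = 0.5147, printed as 0.52.
- Schoenfeld events: 4 x (1.960 + 0.842)^2 / (ln 0.5147)^2 = 31.4 / 0.441 = 71.2, so 72. Power with 72 events is 80.4%. At the rounded 0.52 the result is 74 events, or 79.2% power with 72.
- Expected events with exponential times, uniform one-year accrual and 16% lost over three years (the SAP does not state the period): 72.1.

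The 72 events and 80% power reproduce. They assume no gain from covariates.

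**2. What time since diagnosis can carry.** Six months before screening plus up to 28 days of screening gives about 0 to 7 months at randomization. If uniform over 6 months, the SD is 0.5 / sqrt(12) = 0.144 years. Even an assumed hazard ratio of 2 per year gives a log-hazard SD of only ln 2 x 0.144 = 0.10.

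**3. Power with and without the omitted information.** Cox simulation: 222 men, 3,000 trials per row, three-year failure of 50% in the control arm and about 30% in the treated arm, accrual and loss as in step 1. One standardised normal baseline score stands for the omitted information. Its log-hazard SD is assumed.

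| Log-hazard SD of score | Power, treatment only | Power, score added | Gain (points) |
|---|---|---|---|
| 0.2 | 79.6% | 79.8% | 0.2 |
| 0.3 | 79.7% | 80.6% | 0.9 |
| 0.5 | 80.0% | 83.6% | 3.6 |
| 0.7 | 82.2% | 88.7% | 6.5 |
| 1.0 | 83.8% | 94.3% | 10.5 |

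The gain does not come from a smaller standard error. At SD 0.5 the standard error is 0.245 without the score and 0.247 with it, while the mean log hazard ratio moves from -0.675 to -0.710. The adjusted model estimates a conditional effect that is larger relative to its standard error.

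Adding a non-prognostic time-since-diagnosis term changed power by 0.3 points or less. With no treatment effect and the score left out, the rejection rate was about 4.5% (2,000 trials). Monte Carlo error on the powers is about 0.4 to 0.8 points.

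**4. Chance imbalance.** For a standardised baseline, the difference between arms of 111 has SD sqrt(2/111) = 0.134, with 95% limits of +/-0.263. The shift in the unadjusted log hazard ratio is about beta x 0.263, where beta is the assumed log hazard ratio per SD.

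| beta | Shift | Hazard ratio, from 0.515 | Power at 72 events |
|---|---|---|---|
| 0.3 | 0.079 | 0.48 or 0.56 | 88% or 70% |
| 0.5 | 0.132 | 0.45 or 0.59 | 92% or 62% |

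The shift is as likely to favour enzalutamide as to count against it.

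**5. Parameter count.** Treatment 1, risk 1, biopsy type 1, age 1, race 2 (three groups in 7.8) and time since diagnosis 1 give 7. Adding two gives 9, or 72/9 = 8 events per parameter. Adding two and removing time since diagnosis gives 8, or 72/8 = 9.

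**The case against.** The case for leaving the models alone has real force.

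- **PSA and Gleason are not ignored.** A reader might infer that they are. The risk group is in every model and is built from T stage, PSA and Gleason. Gleason 3+4 can occur only in the intermediate stratum, so a separate Gleason term would be largely redundant. This stands. What is missing is percent positive cores altogether, and the variation in PSA within a stratum.
- **Time since diagnosis does not waste power.** A reader might infer that it is nearly constant and displaces something better. It spans about 0 to 7 months, and keeping it costs 0.3 points or less. The loss, if any, comes from the omission.
- **The gains rest on assumptions.** The comparator was a treatment-only model, whereas the SAP already adjusts for risk group, biopsy type, age, race and site. Only information beyond those counts. The simulation also had no strata, site effect or interval censoring. This stands, and the table should be read as an upper end.
- **The direction is uncertain.** A high share of positive cores at entry leaves less room for a further rise, even if it makes upgrading or therapy more likely. The entry biopsy may have only 10 cores against 12 systematic cores later, which adds noise. Both points could shrink the gain; neither makes adjustment harmful.
- **The positive-cores model is weak precedent.** Section 7.4.2.3 speaks of a composite score and asks for 3- and 6-month comparisons, although cores are assessed only at screening, 12 and 24 months. It does not clearly show that the SAP adjusts for baseline cores, and the point does not rest on it.

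**Conclusion.** The point holds as an improvement to a valid analysis. The covariate lists in 7.4.1, 7.4.1.1 and 7.4.2.1 contain neither baseline percent positive cores nor continuous baseline PSA, although the endpoints are judged against these measures or plausibly depend on them.

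A reader might go further and conclude that the trial is underpowered or the primary test unsound. The documents do not support that: the 72 events and 80% power reproduce without any covariate gain, the type I error is kept, and randomization is stratified by risk and biopsy type.

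For the primary comparison the forgone power is about 0 to 1 point if the omitted information is weak (log-hazard SD 0.2 to 0.3), 4 to 7 if moderate (0.5 to 0.7) and about 10 if strong (1.0). These are upper-end figures, and the SAP gives nothing to choose among them. The gain in the negative-biopsy and PSA models is not quantified here.

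**What to change.** - **7.4.1 and 7.4.1.1:** add centrally read baseline percent positive cores and log baseline PSA as fixed effects.
- **7.4.2.1, negative biopsy:** add baseline percent positive cores.
- **7.4.2.1, PSA rise and time to PSA progression:** add log baseline PSA. Time to PSA progression takes its methods from 7.4.1 by reference, so state its covariates explicitly.
- **Gleason:** no separate term is needed.
- **Time since diagnosis:** keep it or, to hold the count at about 8 parameters for 72 events, move it to a sensitivity analysis. Section 8 names age and site as additions to the protocol, so time since diagnosis may come from the protocol model. If it is moved, list that there as a departure, together with the new terms.
- **Missing baselines:** 7.10.1 imputes nothing in general, so a man without a baseline value would drop out of the adjusted FAS model. Prespecify a simple rule that does not use the treatment arm, such as substituting the median of his risk stratum.

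The cost is a few words and one or two parameters. No new data are needed: Table 2 and Section 3.2 already provide for central reading of the entry biopsy and central PSA. The change should be made before results by arm are seen, since added later it would be post hoc.

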## 8 SAP DEPARTURES FROM THE PROTOCOL

- [REDACTED] *CCI*  
[REDACTED]
- Primary and secondary analysis will be done separately for therapeutic and pathological progression, in addition to overall.
- FAS and SAF would be different in the case of subjects randomized to enzalutamide treatment group end up discontinuing before taking a single dose of the study drug
- It is unlikely but possible to have dose increases. Such a possibility has been accounted for in the relevant table and listing.
- “Age” will be an additional fixed effect used in the statistical models.
- “Site” will be an additional random effect used in the statistical models.
- [REDACTED] *CCI*
- ENACT study is conducted in patients with localized disease who are candidate for Active Surveillance, the use of questionnaire such as BFI, SF-12, MAX-PC and EPIC have not been validated in this patient population, as a result analysis of PROs will be limited to descriptive statistics. The details of descriptive analyses can be found in respective PRO sections.
- All analyses will be performed separately by stratification factors [prostate cancer risk (low/intermediate) and type of biopsy performed (mpMRI targeted/non mpMRI targeted)].

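### Kaplan-Meier for pathological progression alone treats earlier primary therapy as ordinary censoring, although it is a competing event, and so modestly overstates the pathological risk in each arm

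*SAP*

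**What the plan says.** The primary endpoint in SAP Section 7.4.1 is a composite of pathological and therapeutic progression. It is summarised by Kaplan-Meier medians, or the 25th percentile if fewer than half of the men progress, with Kaplan-Meier plots and a Cox model. The section then states that "the primary and secondary analyses will be repeated for pathological progression and therapeutic progression, individually". Section 8 lists this as a departure from the protocol: "Primary and secondary analysis will be done separately for therapeutic and pathological progression, in addition to overall".

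Sections 6.4 and 7.4.1 give one set of censoring rules. Men without progression at trial completion, discontinuation or death are censored at their last assessment, and men who switch therapy are censored at the first switch. For the Cox model, "Censoring assumptions will follow the same rules as applied for the KM estimates". No rule is specific to a component, and the SAP does not mention competing risks or cumulative incidence.

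Three other statements bear on the point:

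- Section 6.4 defines therapeutic progression as the first primary therapy (surgery, radiation, focal or systemic).
- Section 3.2 schedules biopsies at 12 and 24 months, and recommends but does not require one when a man is considering intervention.
- Section 7.4.1.1 plans simple percentages with progression at one year, two years and study completion, also by component.

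**The concern.** In the composite, therapy is an event and nothing is lost. Once pathological progression stands alone, therapy no longer counts as an event, and the only rules available turn it into a censoring time. Kaplan-Meier treats a censored man as someone who could still show the event later, with the same risk as those who remain. After a prostatectomy he cannot show progression on a surveillance biopsy. One minus Kaplan-Meier then describes a setting in which nobody receives therapy, not the proportion of men who will be found to have progressed.

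The component matters to the reader. The trial is open label, so the decision to treat may be influenced by knowledge of the arm, whereas Section 3.2 has biopsies read centrally by a pathologist blinded to allocation. The pathological component is therefore the one less open to that influence, and its curves and percentiles should show the actual risk. The report could also carry two differing pathological risks, one from Kaplan-Meier and one from the simple percentages of Section 7.4.1.1, with no explanation of the gap.

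**Working it through.** **Inputs from SAP Section 4.** Composite progression rates per year: 0.2310 (AS) and 0.1189 (enzalutamide). Type I error: "The overall two-sided type I error for this study is set at 0.05 level". Power 80%. Design: "A sample size of 222 subjects randomized in a 1 to 1 manner accrued over one year, a study duration of 3 years". Loss to follow-up 16%. Effect: "an assumed underlying hazard ratio of 0.52"; the two rates give 0.1189/0.2310 = 0.5147.

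**The plan's own figure.** Schoenfeld events = 4 × (1.960 + 0.842)² / (ln HR)². With HR 0.5147 this is 71.2, rounded up to 72; with the rounded 0.52 it is 73.4, rounded up to 74. Expected events with 111 men per arm, uniform one-year accrual and 16% loss spread exponentially over three years come to 72.1. The stated 72 reproduces, so the rates are a fair base.

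**Assumption.** The SAP does not say what share *s* of first progression events is therapy without prior pathological progression. I take *s* from 10% to 50%, the same in both arms, with constant hazards.

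**Direction.** At each event time both estimators multiply the pathological hazard by a survival term. Kaplan-Meier uses survival free of pathological progression only. Cumulative incidence uses survival free of pathological progression and therapy, which cannot be larger. So 1-KM is never below the cumulative incidence, whether or not therapy is related to prognosis.

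**Size at 2 years, continuous detection.** For composite rate λ, 1-KM = 1 − exp(−(1−s)λ·2) and cumulative incidence (CIF) = (1−s)(1 − exp(−λ·2)). For example, AS at s = 50%: 1 − exp(−0.2310) = 20.6% against 0.5 × (1 − exp(−0.4620)) = 18.5%.

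| s | AS 1-KM | AS CIF | Excess | Enza 1-KM | Enza CIF | Excess |
|---|---|---|---|---|---|---|
| 10% | 34.0 | 33.3 | 0.7 | 19.3 | 19.0 | 0.2 |
| 20% | 30.9 | 29.6 | 1.3 | 17.3 | 16.9 | 0.4 |
| 30% | 27.6 | 25.9 | 1.7 | 15.3 | 14.8 | 0.5 |
| 50% | 20.6 | 18.5 | 2.1 | 11.2 | 10.6 | 0.6 |

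Excesses are percentage points, taken before rounding.

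**Size at 2 years, detection only at the 12- and 24-month biopsies.** With h = 1 − exp(−(1−s)λ) per year, 1-KM = 1 − (1−h)² and CIF = exp(−sλ)h + exp(−2sλ)(1−h)h. The excess is 1.1 to 3.2 points (AS) and 0.3 to 0.9 points (enzalutamide). AS at s = 50%: 20.6% against 17.4%.

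**Arm difference at 2 years, continuous detection.** At s = 50%: 20.6 − 11.2 = 9.4 points by 1-KM against 18.5 − 10.6 = 7.9 by cumulative incidence. At s = 20%: 13.6 against 12.7. Under these assumptions the error widens the difference in favour of enzalutamide, because the AS event rate is higher.

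**25th percentile, AS arm, continuous detection.** At s = 20%: 18.7 months by Kaplan-Meier against 19.5 by cumulative incidence. At s = 50%: 29.9 against 36.0.

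**The case against.** The strongest reply is that little is at stake. These are supportive analyses in a study that the SAP calls exploratory. The group comparison rests on the Cox model, which remains interpretable. Section 7.4.1.1 already gives component percentages that do not censor at therapy: a man treated first counts as without pathological progression, so apart from dropout they are close to cumulative incidence. Biopsy before intervention is recommended and therapy after pathological progression does not compete, so the therapy-first share may be at the low end. All of this stands and limits the size and weight of the point. It does not make the planned curves and percentiles correct.

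Two premises are inferences. The SAP does not say that therapy ends surveillance biopsy; this is plain for prostatectomy and less so for focal or systemic therapy. Nor does it define switching therapy. If treated men stayed in the risk set until study discontinuation, most of the overstatement would disappear. Censoring at therapy start is the plain reading, not an explicit rule.

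A reader might also infer four stronger things that the SAP does not support:

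- **The primary result is biased by this.** It is not by this mechanism, as long as therapy counts as an event in the composite.
- **The therapeutic-only analysis wrongly drops men at pathological progression.** No listed rule censors there, so read literally they stay at risk. Only an explicit confirmation is missing.
- **1-KM risks for the components that add up to more than the composite prove an error.** They do not. If men are followed for therapy after pathological progression, the components overlap, and correct cumulative incidences can also exceed the composite in sum.
- **The 3-year excess is the relevant size.** It is larger (1.4-4.3 points AS, 0.5-1.3 enzalutamide), but scheduled biopsies end at 24 months, so two years is the fair horizon.

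**Conclusion.** The point holds in a limited form. On the plain reading of Section 7.4.1, the pathological-only Kaplan-Meier curves and percentiles censor a competing event and overstate the actual risk in each arm. The direction is certain once therapy start is censored; the size is modest. In relative terms the 2-year excess runs from about 1% (enzalutamide, 10% share, continuous detection) to about 18% (AS, 50% share, biopsy-only detection).

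These sizes rest on the SAP's planning rates, constant hazards, and an assumed therapy-first share that is equal in both arms. If the shares differ between arms, as they may in an open-label trial, the effect on the arm difference will differ from the figures shown. The matter is worth correcting before analysis but does not threaten the trial's main conclusion.

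**What to change.** In Section 7.4.1, state separate rules for the component analyses:

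- **Pathological progression alone:** replace the Kaplan-Meier curves and percentiles with Aalen-Johansen cumulative incidence by arm, with therapy start and death as competing events. Label the Cox result a cause-specific hazard ratio.
- **Therapeutic progression alone:** use cumulative incidence with death competing, and confirm in the text that follow-up continues through pathological progression.

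The cost is a few lines of SAP text and a small amount of extra programming. No new data are needed, and the composite analysis does not change.
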